5.5 Primary Endpoint

Incidence of enlarged clinically palpable groin nodes (groin metastasis) in women randomised to serial high-resolution groin USM compared to surgical groin LND 12 months after surgery.

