| Study Objectives | 
Primary objective:
 
 To determine the incidence of palpable, fixed to skin and histologically positive groin nodes at 12 months in women with vulvar cancer randomised to serial high-resolution groin USM versus standard surgical groin LND 
Secondary objectives:
 
 Compare Patient Reported Outcomes (PROMS) and Health-Related Quality of Life (HRQL) between the groups Compare pain and adverse events (morbidity) between the groups Compare lower limb lymphoedema between the groups Compare cost and cost effectiveness between the groups Determine the diagnostic accuracy of pre-operative, standardised high-resolution groin ultrasound to identify groin node metastasis. 
Translational research objective:
 
 To assess the role of blood and tissue molecular biomarkers to accurately determine the burden of disease (positive lymph nodes) in vulvar cancer, assist with risk stratification and aid disease surveillance |
| Study Endpoints | 
Primary endpoint:
 
 Incidence of clinically palpable, fixed to skin and histologically positive groin lymph nodes (node metastasis) at 12 months after surgical excision of the primary vulvar tumour |

| | |

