3.2 Importance of Groin Nodes

Vulvar cancer develops from vulvar skin. It can spread locally to adjacent structures (vagina, urethra, anus) or via lymphatic channels to regional lymph nodes in the groin [2, 5]. If groin nodes are involved, the cancer is upgraded to Stage 3. This indicates a worse prognosis compared to tumours confined to local involvement [4]. Patients with groin node metastasis require further treatment. Unfortunately pre-treatment detection via groin clinical examination (palpation) and medical imaging scans do not reliably detect microscopic groin node involvement [2, 5]. Hence current clinical guidelines mandate that all patients (except those with Stage 1A disease) require surgical groin LND to mitigate the risk of missing groin node metastases [12]. In 30% of cases (~120 Australian women per year) a groin LND reveals positive (involved) nodes [8, 9], and a concomitant need for postoperative radiation treatment. Should positive groin nodes be missed and become enlarged and clinically palpable, more than 90% of patients will die within 12 months despite subsequent treatment [2, 5]. Conversely, if groin node involvement is detected early while still small, survival outcomes are expected to be excellent. For those reasons, the detection of clinically palpable, enlarged groin nodes is an appropriate marker for oncological safety in vulvar cancer (primary outcome of this clinical trial).

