5.1 Primary Research Question

Is incidence of groin metastases (defined as enlarged, clinically palpable, fixed to skin and histologically positive nodes) comparable between women randomised to serial groin USM or upfront groin LND?

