5.3 Primary Objective

Determine the incidence of palpable, fixed to skin and histologically positive groin nodes in women with vulvar cancer randomised to serial high-resolution groin USM compared to standard upfront surgical groin LND at 12 months.

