11.1 Sample Size & Stopping Rules

Incurable groin recurrence has a >90% mortality within 12 months [21]. We estimate the probability of incurable groin recurrence within 12-month of an upfront LND, i.e., $P(\text{recur}|\text{LND})$, to plausibly be up to 3% in usual practice. This is based on a 32% prevalence of positive nodes in clinical stage I/II vulva cancer [41] and that the false negative rate for routinely used SNB is up to 8.8% [7,42]. A

recurrence probability given groin USM, i.e., $P(\text{recur}|\text{USM})$, of 6% would be acceptable to avoid the side-effects of LND based on our decision analysis using best available evidence, expert judgement, and consumer input. $P(\text{recur}|\text{USM})$ will be characterised using a Bayesian Beta-Binomial model with priors informed by our pilot study (1/32 recurrences) [10]. We will declare groin USM acceptably safe if the probability that $P(\text{recur}|\text{USM}) < 0.06$ is 80%. A Bayesian Monitoring approach will ensure participant safety (MD Anderson Biostatistics BTOX routine www.trialdesign.org/#software). Stopping early due to unacceptably safety will be triggered if there is more than a 70% probability that $P(\text{recur}|\text{USM})$ exceeds 0.06 (i.e., recurrence rate of at least 5/40, 6/60, 7/80, 9/100, or 10/120). We anticipate that $P(\text{recur}|\text{USM})$ is truly 3% and thus calculate that ANVU has less than a 2% probability of incorrectly stopping early for unacceptable safety and a 0.85 probability of correctly declaring acceptable safety at N=120. The statistical design accommodates expansion beyond N=120 USM participants (e.g., as a protocol amendment) if neither safety criterion is reached and the predicted probability of success given expansion is at least 80%.

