11.2.1 Incidence of Enlarged, Palpable Groin Nodes

Groin USM will be deemed acceptably safe if the probability that $P(\text{recur}|\text{USM}) < 0.06$ is 80% using the approach described [in section 11.1](#). This will be supplemented by conventional frequentist methods to estimate the proportion of women with clinically enlarged palpable groin node metastases at 12 months from randomisation for each group together with 95% confidence intervals. The difference in proportions between groups will also be calculated and presented with confidence intervals.

11.2.2 Impact of Ultrasound Surveillance on Quality of Life and Function, Pain, Lymphoedema and Morbidity

Demographics, behavioural characteristics and comorbidities will be captured at enrolment (baseline), 8 weeks, 6 months and 12 months, PROMs including HRQL and FoR (only at 12 months) will be assessed by a study-specific survey incorporating validated instruments:

PROMs will be scored according to their manuals to construct scales. Comparisons between randomised groups on PROMs scales will be performed using a linear mixed model for repeated measures accounting for stratification factors. Analysis will also be performed using a time-integrated approach to HRQL outcomes assessment pioneered by [name] [44]. Logistic regression will be used to compare groups on categorical outcomes (or an exact test if there are few events). Categorical outcomes include: return to usual activities at 8 weeks post-surgery; and the proportion of women experience a clinical relevant change in PROMs from baseline [45] at 8-weeks post-surgery, 6 months post-surgery, and 12 months post-surgery.

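### The primary event is defined inconsistently across the endpoint, the 6% rule and safety monitoring, and one differently classified node can reverse the safety conclusion

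*Protocol*

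**What the plan says.** Current protocol text describes the primary event in three ways.

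- **Palpable, fixed to skin and histologically positive.** The synopsis endpoint is "Incidence of clinically palpable, fixed to skin and histologically positive groin lymph nodes (node metastasis) at 12 months after surgical excision". Section 5.1 has "defined as enlarged, clinically palpable, fixed to skin and histologically positive nodes". Section 5.3 has "Determine the incidence of palpable, fixed to skin and histologically positive groin nodes in women with vulvar cancer".
- **Enlarged and palpable, fixation not mentioned.** Section 5.5, the formal endpoint, has "Incidence of enlarged clinically palpable groin nodes (groin metastasis) in women randomised to serial high-resolution groin USM". Section 3.2 says "the detection of clinically palpable, enlarged groin nodes is an appropriate marker for oncological safety in vulvar cancer" and calls this the primary outcome. Section 11.2.1 estimates "clinically enlarged palpable groin node metastases at 12 months from randomisation". Section 12.1 says that enlarged, palpable groin node metastases or recurrences will be monitored against the stopping rules.
- **Incurable groin recurrence.** Section 11.1 begins its design from this event: "We estimate the probability of incurable groin recurrence within 12-month of an upfront LND". The 6% limit, the pilot-based prior (1/32) and the stopping counts follow from it. Section 12.4 monitors the same event on the 11.1 schedule. Neither section defines it by palpability, fixation or histology.

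The 12-month clock starts at surgery in the synopsis and 5.5, and at randomisation in 11.2.1.

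**The concern.** The trial makes one go/no-go decision and applies one set of stopping counts. Both need a single countable event. A palpable, mobile, histologically positive node counts under 5.5, 11.2.1 and 12.1 as written. It does not count under the synopsis, 5.1 or 5.3. Section 11.1 does not say whether it is incurable.

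The error can run either way. Counting broad events against a limit meant for incurable recurrence could stop or reject ultrasound monitoring wrongly. Counting only skin-fixed nodes, when readers understand palpable metastasis, could overstate its safety. Safety monitoring is affected while the trial runs, because 12.1 and 12.4 name different events. The trial is also open label, so an unsettled event leaves room for a choice after results are known.

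**Working it through.** **Inputs (section 11.1).** Limit 0.06; safety declared if the posterior probability of a rate below 0.06 is 80%; stop if the posterior probability of a rate above 0.06 exceeds 70%; stopping counts 5/40, 6/60, 7/80, 9/100, 10/120; prior informed by 1/32; assumed true rate 3%; stated false stop below 2% and correct acceptance 0.85 at N=120.

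**Step 1: reproduce the design.** The prior's parameters are not stated. A Jeffreys prior plus the pilot gives Beta(0.5+1, 0.5+31) = Beta(1.5, 31.5). With x events in n, the posterior is Beta(1.5+x, 31.5+n−x).

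| n | stated count | P(rate > 0.06) at that count | one event fewer |
|---|---|---|---|
| 40 | 5 | 0.805 | 0.656 |
| 60 | 6 | 0.754 | 0.607 |
| 80 | 7 | 0.710 | 0.567 |
| 100 | 9 | 0.784 | 0.670 |
| 120 | 10 | 0.749 | 0.635 |

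All five counts are the smallest that exceed 0.70. At a true 3%, the exact sequential binomial probability of stopping before 120 is 0.017, and P(X ≤ 5 | n=120) = 0.847. These match the stated figures.

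**Step 2: find the pass limit at N=120.**

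- x = 5: posterior Beta(6.5, 146.5), P(rate < 0.06) = 0.859, passes.
- x = 6: posterior Beta(7.5, 145.5), P(rate < 0.06) = 0.758, fails.

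One node classified differently can therefore change the conclusion. The exact limit depends on the inferred prior. Beta(1, 31), for example, would pass 6 (0.807) and fail 7 (0.690), but it does not reproduce the stated 6/60 (0.695) or 7/80 (0.651). Under either prior a single event separates pass from fail.

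**Step 3: vary the counted rate.** Every skin-fixed, histologically positive palpable node is also a palpable node, so the broader count cannot be smaller. How much larger it is cannot be read from the protocol, so the rates above 3% are assumptions.

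| counted rate | P(declare safe), X ≤ 5 of 120 | P(stop before 120) |
|---|---|---|
| 3% | 0.85 | 0.02 |
| 4% | 0.65 | 0.06 |
| 5% | 0.44 | 0.14 |
| 6% | 0.27 | 0.26 |

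**Step 4: time origin.** The baseline ultrasound is up to 30 days before planned surgery (7.3), and randomisation follows it. Losing a full 30 days of postoperative follow-up at constant hazard gives 0.03 × 335/365 = 0.0275, and P(X ≤ 5) moves from 0.847 to 0.885. This is an upper bound on a small effect.

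**The case against.** The best defence is that the shorter wording is shorthand. Section 5.1 defines groin metastases with all components, and 5.5 carries that term in brackets; 11.2.1 and 12.1 also say metastases. Incurable recurrence can be tied to the narrow event as well: section 2 gives more than 90% mortality within 12 months for palpable nodes attached to the skin, and 11.1 gives the same figure for incurable recurrence.

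Part of this stands. The bracket in 5.5 may well imply histology. It cannot safely imply skin fixation, because section 3.2 gives the same mortality for enlarged, palpable nodes without fixation and calls them the primary outcome. The blinded adjudication in 12.5 does not settle it, since that section addresses location and date and gives the committee no primary-event definition.

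Several stronger readings are tempting, but the documents do not support them.

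- **That the definition will decide the result.** No event rate is given by definition, so only can is shown.
- **That the pilot's 3/32 (9.4%) against 1/32 (3.1%) brackets the 6% limit.** The three nodes were detected by ultrasound and are not stated to be palpable or fixed. 9.4% is not the rate of any stated endpoint.
- **That 11.2.1 applies the 6% rule to palpable nodes.** It applies the rule through 11.1. The palpable-node and randomisation wording belongs to the supplementary frequentist estimate.
- **That the prior and limit were set for the skin-fixed definition.** This is inference; the protocol does not describe the 1/32 event in those terms.
- **That the randomisation clock loses the month-12 scan in general.** That holds only when surgery or the visit falls late.
- **That the arithmetic in 11.1 is wrong.** It reproduces.

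**Conclusion.** The point holds as an inconsistency in current text. It should be fixed before the 6% rule or any stopping count is applied, because neither can be applied unambiguously until then. The clear gaps are skin fixation, present in the synopsis, 5.1 and 5.3 and absent from 5.5, 11.2.1 and 12.1, and the undefined event in 11.1 and 12.4.

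Its possible size is large: the pass limit turns on one event in 120, and each assumed percentage point added to the counted rate lowers the chance of declaring safety by about 0.2. This rests on an inferred prior, although one that reproduces every stated design figure, and on an assumed range of rates. The time origin is a minor wording matter.

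**What to change.** The sponsor should choose one event definition and use it in the synopsis, 5.1, 5.3, 5.5, 11.1, 11.2.1, 12.1 and 12.4. Which definition is intended is for the sponsor to settle. The amendment should also:

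- state how incurable groin recurrence and the 1/32 pilot event map to the chosen definition, and confirm that the 6% limit was set for it;
- ensure that the eCRF and the adjudication committee record each component separately, including skin fixation (the follow-up visits in 7.5 list only disease status);
- report the other definition as a supportive endpoint;
- use one time origin, replacing the randomisation clock in 11.2.1 with events up to and including the month-12 post-surgery visit.

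The cost is a wording amendment and possibly one added eCRF field. If the sponsor finds that the limit or prior was set for a different event from the one chosen, the figures in 11.1 would need to be recalculated.

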5.6 Secondary Endpoint

1. HRQL and PROMS as measured by the EQ-5D and FACT-V at baseline, 8 weeks, 6 months, and 12 months
2. Morbidity at 12 months after surgery
3. Lower limb lymphoedema: incidence up to 12 months after surgery
4. Cost and cost effectiveness at 12 months post-surgery
5. Clinical accuracy of high-resolution ultrasound to predict groin lymph node involvement
6. Disease-free survival (DFS) and overall survival (OS)
7. Utility of biomarkers to reliably reflect the presence or absence of positive groin lymph nodes
8. Explore novel biomarkers for vulvar cancer

6. Study Design

A phase II, open label, multicentre, three-group, randomised clinical trial (ANVU).

6.1 Study Population

The following study population will be identified through gynaecological oncology clinics in Australian (QLD, NT, NSW, VIC, TAS, WA, and SA), and international sites.

6.2 Inclusion Criteria

- Females, over 18 years, with histologically confirmed SCC, adenocarcinoma, or melanoma of the vulvar
- Clinically stage 1 or 2 on medical imaging (CT or MRI scan of pelvis, abdomen, and chest), without evidence of regional or distant metastatic disease
- Undergo IFL/SNB according to local clinical practice management guidelines
- Willing and able to comply with all study requirements, timing and/or nature of required assessments.
- Signed written informed consent
- Negative (serum or urine) pregnancy (BHCG) test \leq 30 days of surgery ONLY in pre-menopausal women and women $<$ 2 years after the onset of menopause.

6.3 Exclusion Criteria

- Women with non-invasive vulvar conditions (e.g. non-invasive non-mammary Paget's disease)
- SCC of the vulvar with depth of invasion \leq 1 mm
- Clinical or medical imaging evidence of regional and/or distant metastatic disease
- Serious concomitant systemic disorders incompatible with the study (at the discretion of the investigator)
- Other prior malignancies $<$ 5 years before inclusion, except for successfully treated keratinocyte skin cancers, or ductal carcinoma in situ
- Estimated life expectancy of \leq 6 months

6.4 Randomisation

Eligible participants will be required to provide signed informed consent before being enrolled. Prior to enrolment, each patient will be screened for eligibility according to the inclusion and exclusion criteria. Participants will then receive a bilateral groin node ultrasound, participants who are found to have negative groin nodes will be randomised using a secure online randomisation system 2:1 to groin USM vs standard groin LND:

- ~120 participants will receive radical wide local excision or radical vulvectomy with serial high-resolution bilateral groin USM every 2 months in conjunction with clinical examinations every 3 months (groin lymph nodes are NOT removed).
- ~60 participants will receive radical wide local excision or radical vulvectomy with groin LND (Based on local clinical practice management guidelines.: either a SNB or an IFL).

Randomisation will be stratified by:

- Clinical stage
 - Depth of invasion (1-2 mm)
 - Depth of invasion (2.1-3 mm)
 - Depth of invasion 3.1 + mm
- HPV status
 - HPV positive
 - HPV negative
- Charlson Comorbidity Index ($<$ 5, \geq 5)

- Histological cell type
 - SCC
 - All other cell types (i.e. adenocarcinoma, melanoma).

Participants with a groin node ultrasound that is suspicious/indeterminate will not be randomised but receive standard groin LND (SNB or IFL as appropriate, as per institutional guidelines).

6.5 Intervention

6.5.1 Protocol of Inguino-Femoral Lymphadenectomy/Sentinel Node Biopsy

All participants will receive appropriate surgical excision of the primary vulvar tumour (radical wide local excision or radical vulvectomy).

For participants who receive standard groin LND, patients can have either a full IFL or a SNB (tracer agent not specified) as per institutional guidelines, unilaterally or bilaterally as appropriate. Patients for SNB need to have tumours less than 4 cm in largest diameter and must be unifocal. Sentinel nodes will undergo ultra-staging [1].

6.5.2 Postoperative Adjuvant Treatment:

Patients who have had a full IFL and have one positive node without extracapsular spread require no adjuvant radiation [32]. Patients with 2 or more positive nodes or with any extracapsular spread should have bilateral groin and pelvic radiation [33]. Patients with a positive sentinel node 2 mm or less in diameter may be treated with bilateral groin and pelvic radiation. Patients with a positive sentinel node greater than 2 mm diameter should have a full IFL and adjuvant radiation if they have any further positive nodes identified [34].

6.5.3 Protocol for Groin Ultrasound Examinations:

All groin ultrasound examinations will be performed by registered sonographers with a postgraduate degree in ultrasound recognised by the Australian Sonographers Accreditation Registry. Minimum requirements for ultrasonic machines include a) Linear transducer/s, 7 and 9 MHz frequencies; b) Curved 5 MHz transducer; c) Colour and Power Doppler; d) Standard linear and volumetric measurements; and e) Looped video.

Ten ultrasound criteria will be captured for each identified groin node on a trial specific case report form: (1) shape (globular vs non globular); (2) homogeneity of echo structure; (3) hyper- or hypoechoic areas within the lymph nodes; (4) hilum abnormalities; (5) cortical thickening; (6) nodal grouping; and for the most suspicious or largest lymph node (7) long (L) and short (S) axis (L/S ratio, values of <2 are considered abnormal); (8) perinodal hyperechoic ring (inflammation); (9) cortical interruption (possibility of extra-nodal spread); and (10) nodal vascularity.

An overall assessment will be made by the radiologist into normal or suspicious/positive. Radiologists will send their report to the local PI within 5 working days of ultrasound completion. All sites are required to enter the completed ultrasound eCRF on REDCap within 5 working days of ultrasound completion. Additionally, they must upload a copy of a signed and de-identified ultrasound report to REDCap, where QCGC Research will verify ultrasound completion.

If the participant is randomised to serial groin USM, patients will have surgical excision of the primary vulvar tumour followed by bilateral groin ultrasound every two months and clinical examinations every three months for the 12 months.

If suspicious, indeterminate, or positive nodes or any other concerning indicators are detected, the participant will be referred to either the local PI or the specialist gynaecological oncologist to discuss their options. Depending on the clinical judgment of the clinician, the participant may be recommended for LND (standard treatment) or may opt to continue with bilateral groin ultrasound every two months and clinical examinations every three months (remaining on trial). Participants undergoing LND will no longer need bilateral groin ultrasound and blood collections every two months and clinical examinations every three months. However, their data will still be collected up to the original 12-month point. Data collected will include documentation of the status of disease, AEs, pain level, health status and quality of life and lymphoedema. Please refer to section [10.6.5.1](#), titled 'Evaluating and Reporting Positive Nodes', for further information.

Patients that fail to comply with the serial ultrasound and clinical examination schedule will be removed from the trial and referred back to their gynaecological oncologist for alternative treatment for safety reasons.

7. Project Methodology

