3.3 Outcomes of Groin Lymph Node Dissection

While effective, groin LND inevitably leads to substantial short- and long-term morbidity [2, 5]. Groin LND can be performed as an IFL; removing all groin nodes or SNB to remove selected (one or two) nodes [7-9]. For SNB and IFL, respectively, adverse outcomes include rates of wound breakdown in 11.7% vs 34%; cellulitis 4.5% vs 21.3%; and life-long swelling of the legs (lymphoedema) in 60% of patients [7-9]. The incidence of surgery-related morbidity is higher in patients who undergo IFL [7]. Less invasive SNB, however, is appropriate in only 50% of cases. SNB is also associated with a false negative rate (up to 10%) that increases the risk of undetected nodes (1% vs. 5%) [4, 7]. For the ~70% to 80% of patients who have negative groin nodes (i.e., no cancer within the nodes), groin LND has no clinical benefit and patients still suffer from the potential adverse outcomes of undergoing this procedure.

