7.5 Follow-Up (Visits 4-9)

All enrolled participants, irrespective of treatment group will be followed-up for 12 months. Participants without groin LND will be provided with medical imaging request forms to receive groin ultrasound examinations every 2 months. **Changes in ultrasound patterns from “normal” to “suspicious” will alert the gynae-oncologist and trigger further clinical action, such as groin LND and histological assessment of the groin nodes. Groin USM will not be offered to women who had a groin LND (IFL or SNB) as it is not standard practice for these patients.** If ultrasound scan surveillance following sentinel node biopsy is included in the standard care protocol at any of the study sites, participants randomised to lymph node dissection (LND) can undergo ultrasound scans as part of their standard care, though it is not mandatory for this study.

Participants will be assessed for local, regional, or distant recurrence, quality of life status, and treatment morbidity for 12 months. Data collected will include documentation of the status of disease, AEs, pain level, health status, quality of life and lymphoedema.

Participants randomised to serial groin USM will be seen every 3 months by a gynaecological oncologist or gynaecologist for clinical examination as per routine standard. Participants receiving standard groin LND (either SNB or LND) will be seen at 8 weeks, 3, 6, 9 and 12 months as per standard clinical practice. Follow up will be handed over to the treating gynaecological oncologist after 12 months.

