8.5 Decision-Making Tool

We will use the trial findings to develop a decision-making tool to support patient shared decision-making for groin USM or LND. This tool will be developed to align with the International Patient Decision Aid Standards (IPDAS) recommendations. It will include information about the probability of all important outcomes for each option including palpable groin node metastases and secondary endpoints such as lymphoedema and morbidity, and uncertainty, and support patients to consider their values and preferences for each outcome in order to achieve an informed decision.

In preliminary work, we have used a decision analysis approach to explicitly frame the treatment choice between groin USM and LND as a trade-off between the potential increased risk of nodal recurrence for USM versus the increased risk of lymphoedema and morbidity for LND using a decision tree. We used the decision tree to explore the impact of existing uncertainty about the probabilities of important outcomes and impact on health-related quality of life for each option on the expected value of USM versus LND. We will use the trial findings to build on the decision tree including explicit incorporation of patient preferences. We plan to use the decision tree approach to facilitate the co-development of an ANVU patient decision tool with consumer representatives, gynaecologists, surgeons, nurse consultants, and other stakeholders. Trial participants from Australian sites will be invited to opt in to receive an invitation to participate in a focus group for the development of the decision aid following the completion of their initial 12-month follow-up period.

Three focus groups will be formed, and each group will attend 4 x 2-hour sessions. Group 1 will comprise of 20 consumers previously treated for vulvar cancer. Group 2 will comprise of 20 certified gynaecological oncologists, nurse consultants, sonographers, and cancer service managers. Group 3

will comprise of 20 women randomised to the Intervention Group of ANVU. For equity, the sample will include rural/remote, younger, and older Australians to contribute important perspectives.

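### The LND arm is a locally chosen mix of SNB and IFL, and the planned procedure need not be recorded before allocation, so USM versus SNB is not a protected randomised contrast

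*Protocol*

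**What the plan says.** All references are to the protocol; the SAP is not at hand.

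- **Allocation (6.4).** Women with a negative baseline ultrasound are "randomised using a secure online randomisation system 2:1 to groin USM vs standard groin LND", about 120 to USM and about 60 to LND. The strata are clinical stage (by depth of invasion), HPV status, Charlson index and cell type. Site, tumour diameter, focality and intended groin procedure are not strata, and nothing asks for the intended procedure to be declared before allocation.
- **Control procedure (6.5.1).** In the LND arm, "patients can have either a full IFL or a SNB (tracer agent not specified) as per institutional guidelines, unilaterally or bilaterally as appropriate". SNB is limited to unifocal tumours under 4 cm. Nothing requires SNB in a woman who meets that limit.
- **Morbidity by procedure (3.3).** For SNB and IFL respectively: "wound breakdown in 11.7% vs 34%; cellulitis 4.5% vs 21.3" per cent. The same section says SNB is suitable in half of cases.
- **Ultrasound in controls (7.5).** One sentence states: "Groin USM will not be offered to women who had a groin LND (IFL or SNB) as it is not standard practice for these patients". The next says that, at sites where surveillance after SNB is standard care, "participants randomised to lymph node dissection (LND) can undergo ultrasound scans as part of their standard care". The study schedule (Section 16) lists groin USM for the interventional arm only.
- **Use of the results (8.5).** On the decision tool: "It will include information about the probability of all important outcomes for each option including palpable groin node metastases and secondary endpoints".

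**The concern.** A main aim of the trial is to show how much morbidity USM spares. On the protocol's own figures, the amount depends on which operation is avoided: IFL carries about three times the wound breakdown of SNB (34 / 11.7 = 2.9) and nearly five times the cellulitis (21.3 / 4.5 = 4.7). A pooled USM-versus-LND contrast averages over the two in proportions set by the participating sites.

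The average would matter less if it could be taken apart afterwards. For women who qualify for SNB it cannot. In the LND arm the procedure is seen at surgery; in the USM arm there is no record of which operation was avoided. Setting LND women who received SNB against all USM women would compare a part of one arm, selected on tumour size, focality and site habit, with the whole of the other. The trial is open label, so the choice of operation can also be made after allocation is known.

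At stake is the interpretation of the morbidity, lymphoedema, patient-reported and cost results, and what the decision tool can tell a woman who would otherwise have SNB.

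**Working it through.** **1. The plan's own figures, and whether they are touched.** Section 11.1 gives stopping boundaries of 5/40, 6/60, 7/80, 9/100 and 10/120, under 2% probability of wrongly stopping early, and 0.85 probability of declaring safety when the true USM recurrence rate is 3%. The weight of the pilot prior (1/32) is not stated. Assuming half weight, Beta(0.5, 15.5), with stopping if P(p > 0.06) exceeds 0.70 and success if P(p < 0.06) is at least 0.80 at 120 women:
- all five boundaries are reproduced;
- success requires 5 or fewer events in 120;
- the probability of an early stop is 1.7% and of success 0.847.

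No LND data enter this calculation. The safety decision, the stopping rule and N = 120 do not depend on the SNB/IFL mix.

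**2. LND-arm morbidity by SNB share.** Let s be the share of the LND arm having SNB. With the Section 3.3 rates:
- wound breakdown = 11.7s + 34(1 − s)
- cellulitis = 4.5s + 21.3(1 − s)

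| SNB share s | Wound breakdown | Cellulitis |
|---|---|---|
| 0% | 34.0% | 21.3% |
| 25% | 28.4% | 17.1% |
| 50% | 22.9% | 12.9% |
| 75% | 17.3% | 8.7% |
| 100% | 11.7% | 4.5% |

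From 25% to 75% SNB, the ratios are 28.4 / 17.3 = 1.64 for wound breakdown and 17.1 / 8.7 = 1.97 for cellulitis. These equal the change in apparent saving if the USM rates are near zero. The absolute shift, 0.5 × (34 − 11.7) = 11.2 points and 0.5 × (21.3 − 4.5) = 8.4 points, holds for any USM rate that does not itself vary with the mix. From 25% to 50% SNB, the ratios are 28.4 / 22.9 = 1.24 and 17.1 / 12.9 = 1.33.

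**3. Which procedure-specific contrasts are randomised as the plan stands.**
- *Tumours of 4 cm or more, or multifocal.* Section 6.5.1 rules out SNB, so USM versus IFL in this group, defined by baseline features, is a randomised contrast, although small and unstratified.
- *Unifocal tumours under 4 cm.* LND women may have either procedure. USM versus LND in this group is randomised, but USM versus SNB is not, because the USM women who would have had SNB are not identified.

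**4. Precision if intended procedure is recorded.** At a 50% SNB share, each intended-procedure group has about 60 USM and 30 LND women. With a 3% rate in both arms, the approximate 95% half-width is 1.96 × √[0.03 × 0.97 × (1/60 + 1/30)] = 7.5 points, against 1.96 × √[0.03 × 0.97 × (1/120 + 1/60)] = 5.3 points for the full arms. For wound breakdown with no events under USM, the LND term alone gives 1.96 × √(0.34 × 0.66 / 30) = 17 points in the intended-IFL group and 1.96 × √(0.117 × 0.883 / 30) = 11.5 points in the intended-SNB group. The normal approximation is rough at these counts.

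**The case against.** The strongest reply is that this is a pragmatic comparator. The research question (5.1) is USM against upfront LND, LND is defined as local standard care, allocation is randomised and analysis is by intention to treat. Both arms draw on the same sites and tumours. All of that stands. A reader might infer that the mixed arm biases the trial, or that USM cannot be compared fairly with either procedure. The documents do not support this: the mix limits interpretation and transportability, and USM versus IFL in women who cannot have SNB is already a randomised contrast.

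Other points on that side also stand, wholly or in part:

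- **Section 7.5.** The two sentences can be read as a rule and its exception, and scans that are already site standard care belong to a usual-care comparator. A reader might infer contamination that the trial never sees. That goes too far: Section 11.2.6 collects all health-service use over 12 months, so scans may be counted there. What is missing is an explicit record of their dates and results. The number of sites or women affected is not given.
- **Size.** A reader might say that the apparent saving nearly doubles. That fits cellulitis only, and needs a 75% SNB share, above the 50% that Section 3.3 calls suitable.
- **Place.** Covariates and subgroups can be left to the SAP, no split by procedure received is planned, and the decision tool is not said to pool SNB and IFL. The randomisation form is not shown and may already hold some of these fields.

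The last point does not dispose of the matter. An analysis plan can choose a covariate but cannot recover, without bias, an intention that was not recorded before allocation.

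**Conclusion.** The point holds as a limit on interpretation that is cheap to remove, not as a defect in the randomised comparison or in the safety decision. USM versus a locally chosen LND mix is a valid contrast. USM versus SNB is not protected, because the intended procedure is neither declared before allocation nor a stratum. Over SNB shares of 25% to 75%, the apparent saving moves about 1.6-fold for wound breakdown and 2-fold for cellulitis; over 25% to 50%, about 1.2-fold and 1.3-fold.

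This rests on three assumptions. The Section 3.3 rates carry over to this trial; if part of the SNB–IFL gap reflects who receives each operation, the effect of site choice is smaller. USM event rates are near zero for the ratios. The SNB share is unknown, so a range is shown. Section 3.3 gives a single 60% lymphoedema figure, without a split by procedure, so the effect on lymphoedema, patient-reported outcomes and cost is expected in kind but cannot be sized from the document.

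**What to change.** 1. **Section 6.4.** Before allocation, record for every randomised woman the groin procedure planned if she is allocated LND (SNB or IFL, unilateral or bilateral), with tumour diameter and focality. The Synopsis already requires willingness to undergo IFL or SNB under local guidelines, so the plan can be stated at that point.
2. **Sections 11.2.2, 11.2.3, 11.2.4 and 11.2.6.** Use intended procedure as a baseline covariate in the between-arm comparisons, and report USM versus LND within each intended-procedure group as exploratory.
3. **Section 7.5.** Reconcile the two sentences on groin ultrasound after LND. Log the date and result of any control-arm groin ultrasound so that its extent can be described by arm.
4. **Section 11.2.1.** Keep scanned controls in the difference in proportions. Dropping them would be a post-randomisation exclusion from one arm only.

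The cost is a few fields on the randomisation form, one eCRF line and one covariate. The existing strata, N and the stated 0.85 are unchanged, and no patients or procedures are added. The downside is low within-group precision, which is why those contrasts should be labelled exploratory.
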